1. TABLE OF ABBREVIATIONS

AE	Adverse Event
AMC	Adjusted Mean Change
ANCOVA	Analysis of Covariance
BMI	Body Mass Index
CFB	Change from Baseline
CI	Confidence Interval
CRO	Contract Research Organization
FAS	Full Analysis Set (also referred to as Intent-to-Treat)
I-QOL	Incontinence Quality of Life
MedDRA	Medical Dictionary for Regulatory Activities
n	Number
PPP	Per Protocol Population
PT	MedDRA Preferred Term
RF	Radiofrequency
SE	Standard Error
SOC	MedDRA System Organ Class
SP	Safety Population
SUI	Stress Urinary Incontinence
TEAE	Treatment-Emergent Adverse Event
WHO-DDE	WHO-Drug Dictionary Enhanced

2. INTRODUCTION

Stress urinary incontinence (SUI) is a major challenge for many women particularly those who have experienced child birth or are menopausal. Upwards of 55% of women with a previous vaginal delivery may exhibit signs and symptoms of SUI (Tahtinen 2016). The overarching effects of SUI impact a women's health and quality of life and have been shown to result in depression, social stigma and lack of self-confidence. The need to use an external pad to absorb urine leakage from even normal daily activities such as laughing, or coughing is unsatisfactory and can be extremely inconvenient, and often embarrassing for women.

Currently available treatment options for women are limited. Pelvic floor exercises (such as Kegels) offer some benefit to a percentage of women but compliance and sustained benefit can be issues. More aggressive approaches to manage SUI include pelvic surgery, slings and mesh. These invasive options involve more risk and recovery time and are a last resort for many patients.

The gap between conservative and invasive treatment options for SUI represents an opportunity to address an enormous unmet healthcare need for women. Minimally invasive treatments for SUI would be a highly appealing solution provided they offered a safe, consistent improvement in symptoms without significant time commitment or recovery. Any effective treatment would represent a major advance in women's health.

The Viveve Procedure, SUI protocol, offers a non-surgical alternative to traditional surgery using non-ablative, monopolar radiofrequency (RF) energy to improve SUI. It induces a mild, controlled reaction in the submucosal tissues that stimulates the body to restore collagen, thereby remodeling the tissue without causing scarring.

This Statistical Analysis Plan describes the analyses planned for protocol VI-19-01 Amendment 2 version dated 15April2020, to demonstrate that the active treatment (i.e., Viveve Treatment, SUI protocol) is superior to the sham treatment.

3. OBJECTIVES

3.1. Primary Objective

The primary objective of this single-blind study is to compare the effect of both the Viveve Treatment (RF plus cryogen) and cryogen alone treatment versus sham treatment, using the SUI treatment protocol (220 pulses), in improving mild to moderate SUI, assessed using the 1-hour pad weight test at 5 months post-treatment.

3.2. Secondary Objectives

The secondary objectives of this single-blind study are:

- Efficacy in decreasing the number of incontinence episodes using the 3 day voiding diary from Baseline to 5 months post-treatment.
- Efficacy in decreasing the number of pads utilized using the 3 day voiding diary from Baseline to 5 months post-treatment.
- Efficacy in decreasing the 24-hour pad weight from Baseline to 5 months post-treatment.
- Quality of Life benefits as measured by changes from Baseline to 5 months post-treatment in the Incontinence Quality of Life (I-QOL).
- Safety through 5 months post-treatment

4. VARIABLES

4.1. Response Variables

4.1.1. Primary Endpoints

The primary efficacy endpoint for this trial is:

- Change from baseline (CFB) to 5 months post-treatment in the 1-hr pad weight.

4.1.2. Secondary Endpoints

- CFB to 5 months post-treatment in incontinence episodes as measured with the 3-day bladder voiding diary.
- CFB to 5 months post-treatment in pads utilized as measured with the 3-day bladder voiding diary.
- CFB to 5 months post-treatment in 24-hr pad weight.
- CFB to 5 months post-treatment in I-QOL.

4.1.3. Safety Endpoints

Safety endpoints for this trial include:

- Safety as assessed by adverse event (AE) reporting from the initiation of treatment to study completion for each subject.

5. STATISTICAL ANALYSIS ISSUES

5.1. Populations to be Analyzed

Subjects in the following population could be enrolled in this study: pre-menopausal (≥ 18 age) female subjects with a normal, or abnormal but not clinically significant, physical, pelvic and neurologic exam; 1-hr pad weight at Baseline ranging from ≥ 5 to ≤ 50 g as the net increase from the pre-test pad weight; and at least one incontinence episode per day as determined in the 3-day voiding diary.

5.1.1. Analysis Populations

The analysis populations will consist of subjects categorized into the 3 populations described below.

5.1.1.1 Full Analysis Set

The Full Analysis Set (FAS) is defined as all randomized subjects who have 1-hour pad weight data at both Baseline and 5 months post-treatment. The FAS will be used for all of the efficacy analyses.

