5.1.1.2 Per Protocol Population

The Per Protocol Population (PPP) is defined as all randomized subjects, who receive a complete treatment, and who complete the 5 month study without major protocol deviations. The PPP will be used for confirmatory analysis of the primary efficacy endpoint.

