5.2. Statistical Analysis of Primary Measures

The primary efficacy endpoint for this study is CFB to 5 months post-treatment in 1-hour pad weight test. Analysis of covariance (ANCOVA) will be used, with treatment group and study site as independent variables and Baseline 1-hour pad weight as the covariate. Baseline 1-hour pad weight is defined as the 1-hour pad weight from the Baseline visit (Visit 2). The FAS will be used. Only observed case data will be used; that is, no imputation for missing data will be performed. The adjusted mean change (AMC) and standard error (SE) will be provided for each treatment group, along with the sham-AMC, 95% confidence interval (CI) and p-value for the Viveve Treatment group and for the cryogen alone treatment group. If the data is determined to be non-normally distributed, then a ranked ANCOVA will be used for the analysis.

A confirmatory analysis of the primary efficacy endpoint will be performed using the PPP.

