5.3. Secondary Efficacy Analyses

The secondary efficacy endpoints include the CFB to 5 months post-treatment in total number of incontinence episodes as measured by the 3-day voiding diary, CFB to 5 months post-treatment in total number of pads utilized as measured with the 3-day

voiding diary, CFB to 5 months post-treatment in 24-hour pad weight, and CFB to 5 months post-treatment in I-QOL. The same ANCOVA that was used for the primary efficacy endpoint will be used for each of the secondary endpoints, with the relevant Baseline as the covariate. Baseline for each endpoint is the analogous measurement from the Baseline visit (Visit 2). The FAS will be used, with observed case data only. For each endpoint, the AMC and SE will be provided for all 3 treatment groups, along with the sham-adjusted mean change, 95% CI and p-value for the Viveve Treatment group and the cryogen alone treatment group. If, for any of the endpoints, the data is determined to be non-normally distributed, then a ranked ANCOVA will be used for the analysis.

For all of the secondary efficacy endpoints, a confirmatory analysis will be performed using the PPP.

The analyses described above for the primary and secondary efficacy endpoints will be carried out using SAS (Version 9.4 or above) Proc Mixed.

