5.6. Experiment Design and Randomization

5.6.1. Experimental Design

This is a randomized, single-blind, sham controlled multicenter clinical trial. This study is designed to evaluate the Viveve Treatment (RF plus cryogen, SUI protocol) and

Cryogen only treatment versus sham treatment for the primary efficacy endpoint, 1-hr pad weight test. Approximately 36 subjects (12 per treatment arm) who meet the entry criteria will be randomized on Day 1 in a 1:1:1 ratio to one of the treatment groups. The Viveve Treatment group will receive a therapeutic dose of 90 J/cm² of RF energy plus cryogen cooling, the Cryogen only treatment group will receive a sub-treatment dose of ≤ 1 J/cm² of RF energy plus cryogen cooling, and the sham group will be treated with an unpowered tip (i.e. treatment will be given without turning on the machine).

Subjects will be followed up with at 10 days and 5 months post-treatment. At the Baseline Visit and Month 5 Visit, subjects will be asked to provide a completed 3-Day Bladder Voiding Diary, complete a 24 hour pad-weight test, complete a 1-hour Pad Weight Test and I-QOL questionnaire. The subjects will be assessed for AEs at all study contacts and visits from the time the patient begins the treatment at the randomization visit.

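### The Full Analysis Set is called intent-to-treat but admits only subjects with a 5-month 1-hour pad weight; this discards usable secondary data, and no planned analysis tests the primary result against missing outcomes

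*SAP*

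**What the plan says.** - **Label.** SAP Section 1 expands FAS as "Full Analysis Set (also referred to as Intent-to-Treat".
- **Definition and use.** Section 5.1.1.1 limits the set to "all randomized subjects who have 1-hour pad weight data at both Baseline and 5 months post-treatment", and adds: "The FAS will be used for all of the efficacy analyses".
- **Primary analysis.** Section 5.2: "Only observed case data will be used; that is, no imputation for missing data will be performed". Section 5.7 leaves missing values missing and does not replace subjects who discontinue.
- **Secondary analyses.** Section 5.3: "The FAS will be used, with observed case data only". It then states: "For all of the secondary efficacy endpoints, a confirmatory analysis will be performed using the PPP".
- **Per Protocol Population (PPP).** Section 5.1.1.2 requires a complete treatment and subjects "who complete the 5 month study without major protocol deviations". It does not name the 1-hour pad test as a condition.
- **Robustness.** Section 5.9 only refers back to the analyses in Sections 5.2 and 5.3.
- **Schedule.** Section 5.6.1 places the efficacy assessments at two visits: "At the Baseline Visit and Month 5 Visit, subjects will be asked to provide a completed 3-Day Bladder Voiding Diary", together with both pad tests and the I-QOL.
- **Baseline tables.** Section 5.10 summarizes baseline characteristics for the FAS. Disposition, with withdrawals and reasons, is tabulated by arm.

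**The concern.** An intent-to-treat set is fixed by randomization. This one is fixed by whether the primary outcome was observed five months later, so the label contradicts the definition, and a reader may take an observed-case result for an intent-to-treat result.

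Two consequences follow. First, with 12 subjects per arm, the loss of one or two whose outcome differs from the rest can move the primary contrast, and nothing planned would show it. Second, a single missing 1-hour test removes a subject from analyses of the diary, 24-hour pad weight and I-QOL, even if she supplied all of those. Because the PPP has no pad-test condition, she may still enter the per-protocol secondary analysis. The per-protocol set could then hold subjects whom the set called intent-to-treat excludes.

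**Working it through.** **1. The plan's own figure.** Section 5.5 gives about 70% power at effect size 1.06 and about 80% at 1.19, with 36 subjects randomized 1:1:1. For a two-sample t-test with n = 12 per arm, two-sided alpha 0.05 and 22 degrees of freedom, the noncentrality is d / √(1/12 + 1/12). The resulting power is 69.9% and 79.6%, so the figures reproduce, but only with all 12 per arm evaluable. If the same number is missing in both arms:

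| Missing per arm | Power at 1.06 | Power at 1.19 |
|---|---|---|
| 0 | 69.9% | 79.6% |
| 1 | 65.7% | 75.6% |
| 2 | 61.1% | 71.1% |
| 3 | 56.1% | 65.9% |

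**2. Who is excluded, endpoint by endpoint.**
- *Primary.* Efficacy is measured only at Baseline and Month 5 (5.6.1), and a Baseline 1-hour value is an entry condition (5.1). A subject outside the FAS has no change score, so the observed-case ANCOVA would omit her anyway. The definition adds no loss.
- *Secondary.* Sections 5.1.1.1 and 5.3 together drop a subject who has her own endpoint's baseline and 5-month values but no 5-month 1-hour test. The cost is 1/12 = 8% of an arm per subject, on each of the four endpoints for which she has data.
- *Per protocol.* Completion is required here too, so comparing the PPP with the FAS says nothing about subjects who left.

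**3. How far missing outcomes could move the primary contrast.** The SAP states no dropout rate, so the loss patterns are assumptions. Inputs: 12 per arm and SD 15 (5.5, 5.6.1), no true effect. Simulation of one active arm against sham, unadjusted t-test, 200,000 trials:

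| Loss pattern | Bias favouring active | Significant benefit (one-sided; nominal 2.5%) |
|---|---|---|
| None | 0 g | 2.5% |
| One or two at random, one active arm | 0 g | 2.5% |
| Worst one, both arms | 0 g | 3.6% |
| Worst one, active arm only | 2.22 g | 5.9% |
| Worst two, active arm only | 4.11 g | 10.6% |

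On the two-sided scale of Section 5.8, the last two rows are about 7% and 11% against 5%. Relative to the 15.9 g difference in Section 5.5, 2.2 / 15.9 = 14% and 4.1 / 15.9 = 26%.

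Under the planned three-arm ANCOVA (assuming two sites, baseline uniform on 5 to 50 g, and baseline-change correlation 0 / -0.3 / -0.6; 40,000 trials per cell):
- worst one lost: 2.26 / 1.97 / 1.51 g, one-sided rate 5.7 / 5.3 / 4.9%;
- worst two lost: 4.19 / 3.76 / 2.74 g, one-sided rate 9.9 / 9.4 / 7.6%;
- random loss: about 0 g, 2.2 to 2.6%.

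**4. Which check would reveal it.** Suppose the worst outcomes are lost.
- *Imputing no change* shrinks the bias only by the fraction observed: 2.22 × 11/12 = 2.03 g, and 4.11 × 10/12 = 3.43 g.
- *Imputing the arm mean plus a penalty delta* shifts the arm mean by (number missing / 12) × delta. The bias is cancelled at delta = 2.22 × 12 = 26.7 g with one lost, and 4.11 × 12 / 2 = 24.7 g with two lost. A range of 0 to 30 g (2 × SD 15) covers both.

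**The case against.** The strongest reply is that the primary analysis is openly described as observed-case. The intent-to-treat wording appears only in the abbreviation table, and the definition costs the primary endpoint nothing. With one post-baseline visit, an observed-case ANCOVA is not wrong in itself if loss is random given the model terms. All of this stands; it narrows the primary-endpoint defect to the label and the missing check.

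The bias figures are also an extreme: the very worst outcomes lost from one active arm and none from sham. That stands too. If loss is only partly related to outcome (assumed latent correlation 0.3), the bias is about 0.3 × 2.22 = 0.7 g or 0.3 × 4.11 = 1.2 g, small beside a standard error of 15 × √(2/12) = 6.1 g. The figures are therefore a bound, not a forecast.

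Secondary exclusions should be uncommon, since all assessments belong to the same visit, and Section 5.8 treats secondary p-values as descriptive. This limits the harm but gives no reason to keep a condition that serves no purpose. Whether a missed 1-hour test counts as non-completion or a major deviation may be settled in the protocol, so the per-protocol overlap is a possibility rather than a certainty. Section 5.10 also fixes population membership before unblinding, a real safeguard against selective exclusion, though not against dropout bias.

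Finally, a tipping-point analysis is one choice among several. Imputation from 10 or 11 subjects per arm is imprecise. The analysis is empty if nobody is missing, and worsening the active arm cannot overturn a non-significant result. None of these points supplies the check that the plan lacks.

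**Conclusion.** The concern holds and should be fixed. The text settles three points: the label contradicts the definition, the 1-hour condition carries into every main secondary analysis, and the only robustness analysis is itself confined to completers. In addition, baseline summaries restricted to the FAS leave the profile of lost subjects out of the summary tables, although disposition counts them by arm.

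The size depends on losses for which the SAP gives no assumption. For the primary contrast it runs from 0 g under random loss to an upper end of 2.2 g (one lost) or 4.1 g (two lost) in the unadjusted comparison. Under the planned ANCOVA the upper end is 1.5 to 2.3 g or 2.7 to 4.2 g, given the assumed sites and correlations. For secondary endpoints the cost is 8% of an arm per subject needlessly excluded, probably in few cases.

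**What to change.** 1. Section 5.1.1.1: define the FAS as all randomized subjects, analysed as randomized.
2. Sections 5.2 and 5.3: for each endpoint, analyse every FAS subject who has that endpoint's own baseline and 5-month values. Delete the 1-hour condition for secondary endpoints and show n per endpoint.
3. Describe the primary analysis as observed-case, and do not present it as intent-to-treat.
4. Section 5.10: summarize baseline for all randomized subjects.
5. Section 5.9: add one delta-adjusted tipping-point analysis of the primary endpoint on all randomized subjects. Impute missing 5-month values from arm, site and baseline. Then worsen the active-arm imputations by 0 to 30 g in 5 g steps, and report the delta at which each active-versus-sham conclusion changes. If the ranked ANCOVA is used, rank after imputation. Missing-at-random imputation or a no-change value alone would not remove outcome-dependent bias.
6. Reconcile Section 5.1.1.2, which assigns the PPP to the primary endpoint, with Section 5.3, which also uses it for the secondary endpoints.

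The cost is SAP wording and one or two extra tables, with no new data. Denominators will differ between secondary endpoints, and the sensitivity result may be less favourable than the observed-case one. The change should be made before unblinding.

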5.8. Multiple Comparisons/Multiplicity

In this study, the Type 1 error is controlled at 0.05 two-sided for the primary efficacy endpoint.

The secondary efficacy endpoints will be compared to a significance level of 0.05 two-sided. No adjustment will be made for multiplicity for these endpoints. Given the number of comparisons, all p-values for secondary efficacy endpoints will be considered descriptive.

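### The secondary endpoints are analysed only in subjects with a 1-hour pad weight at Month 5, so valid secondary data can be discarded because a different test is missing

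*SAP*

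**What the plan says.** SAP section 5.1.1.1 makes FAS membership depend on having a 1-hour pad weight at both Baseline and Month 5, and gives the set a general role: "The FAS will be used for all of the efficacy analyses". Section 5.3 repeats this for the secondary endpoints: "The FAS will be used, with observed case data only". Those endpoints are changes from Baseline to Month 5 in diary incontinence episodes, diary pads used, 24-hour pad weight and I-QOL (section 4.1.2). Each is fitted with the primary ANCOVA, "with the relevant Baseline as the covariate".

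Three other places bear on the point:

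- Section 5.6.1 lists the assessments at Baseline and Month 5 as separate items: "subjects will be asked to provide a completed 3-Day Bladder Voiding Diary, complete a 24 hour pad-weight test", then the 1-hour test and the I-QOL.
- Section 5.3 adds a supportive analysis: "For all of the secondary efficacy endpoints, a confirmatory analysis will be performed using the PPP". Section 5.1.1.2 defines the Per Protocol Population (PPP) by complete treatment and by subjects "who complete the 5 month study without major protocol deviations", not by 1-hour pad data.
- Section 5.8 states that "all p-values for secondary efficacy endpoints will be considered descriptive".

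**The concern.** The observed-case rule already drops any subject who lacks the endpoint being analysed. Requiring a 1-hour pad weight on top of that can only remove subjects who do have the endpoint. A woman who returns her diary, completes the 24-hour pad test and fills in the I-QOL at Month 5, but whose 1-hour test is missed or unusable, is excluded from all four main secondary analyses. The abbreviation list in section 1 equates the FAS with intent-to-treat, so a reader of the secondary tables would expect every randomized subject with data on that endpoint to be there.

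At stake are the precision of the secondary estimates and confidence intervals in a very small trial and, possibly, some added selection, because inclusion depends on a post-randomization result of another test. Since the secondary p-values are descriptive, the estimates and intervals carry most of what these endpoints can show.

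**Working it through.** **The plan's own figures.** The SAP gives no power or precision for the secondary endpoints. Its only such figures (section 5.5) concern the primary endpoint: about 70% power at an effect size of 1.06 and about 80% at 1.19, with 12 per arm. A two-sample t-test calculation at two-sided 0.05 gives 69.9% and 79.6%, so these reproduce. The present point does not depend on them.

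**Who is affected.** The rules, taken case by case:

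1. *No 1-hour weight at Baseline.* This should not arise among eligible subjects, because section 5.1 has an entry range for it ("1-hr pad weight at Baseline ranging from" 5 to 50 g). In practice the Month 5 test decides FAS membership.
2. *Whole Month 5 visit missed.* No Month 5 secondary data exist, so the subject is lost under either rule.
3. *1-hour test present, a secondary measure missing.* The subject is in the FAS but drops out of that secondary analysis as a non-observed case, under either rule.
4. *Secondary measure present, Month 5 1-hour test missing or unusable.* The subject is excluded under the SAP and would be included if the population were set by endpoint. This is the only case in which the rules differ.

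A case 4 subject might still enter the supportive PPP analysis if the missed test is not classed as a major deviation, which the SAP does not state. She could then be in the supportive set but not in the main one.

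**Effect on precision.** Inputs: 12 per arm (section 5.6.1), and a common SD that cancels. Adjustment for covariate and site is ignored. With *a* and *b* subjects left in the two compared arms,

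SE ratio = √[(1/a + 1/b) / (1/12 + 1/12)]

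| Case 4 subjects lost (assumed) | a, b | SE ratio | SE wider by |
|---|---|---|---|
| none | 12, 12 | 1.000 | 0% |
| one, in one arm | 11, 12 | √1.0455 = 1.022 | 2.2% |
| one in each arm | 11, 11 | √1.0909 = 1.044 | 4.4% |
| two, in one arm | 10, 12 | √1.1 = 1.049 | 4.9% |
| two in each arm | 10, 10 | √1.2 = 1.095 | 9.5% |

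One subject is 1/12 = 8.3% of an arm.

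**Effect on the estimate.** If one omitted subject's change differs by k SD from the mean of the other 11, restoring her moves the arm mean by k/12 SD. For an assumed k = 1 this is 0.083 SD. For scale, the SE of a difference with 12 per arm is √(2/12) = 0.41 SD, so the shift is about one fifth of a standard error (0.083/0.41 ≈ 0.20).

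**The case against.** The strongest reply is that the harm is hypothetical. The four instruments and the 1-hour test belong to the same visits, so most subjects will have all of them or none, and the SAP gives no reason to expect anyone to miss the 1-hour test alone. If one subject did, the loss of precision would be about 2% and the illustrated shift well inside the noise. The two-per-arm row needs four of the 24 compared subjects to miss only that test, which nothing in the document supports. No confirmatory conclusion rests on the secondary endpoints, the SAP claims no power for them, and the PPP repeat may recover some of the data. A single efficacy set also has a recognisable merit: the secondary results then describe the subjects behind the primary result.

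Most of this stands, and it limits the weight of the point. The number affected may be zero, the table is illustrative, and the document offers no mechanism that would tie a missed 1-hour test to treatment or outcome, so selection is only a possibility. Two parts do not rescue the rule. The PPP analysis is supportive, and whether it would include such a subject is not settled. The appeal to a common set is weak because observed-case analysis already lets N differ between the secondary tables.

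**Conclusion.** The point holds. As written, sections 5.1.1.1 and 5.3 exclude from the main secondary analyses any subject who lacks only the Month 5 1-hour pad weight, and nothing else in the SAP overrides this. The restriction has no function in models that do not use the 1-hour value.

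Its size depends on a count the document does not give. At zero subjects nothing changes. At one or two per affected arm, the standard error of a difference widens by roughly 2% to 10%, on the assumptions of a common SD and no covariate or site adjustment. The primary analysis is untouched. The change should be made because it keeps data already collected at almost no cost, not because a material distortion is expected.

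**What to change.** Amend SAP sections 5.1.1.1 and 5.3 so that the FAS as now defined applies to the primary endpoint only. Each secondary endpoint would be analysed in all randomized subjects, as randomized, who have that endpoint at Baseline and at Month 5, whether or not a 1-hour pad weight is available. The current FAS version can be kept as a supplementary table for anyone who wants the primary and secondary results on the same eligibility rule.

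The cost is one sentence. The only drawback is that N may differ between the primary and secondary tables, so each table should show its own N. The change belongs before unblinding, when section 5.10 has subjects assigned to populations, so that it cannot look like a post hoc choice.
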